A single-center, double-blind, parallel-group, placebo-controlled randomized trial.

B. Outcomes

1) Primary outcome:

- i. Presence of ischemic stroke or TIA (Transient Ischemic Attacks) assessed by symptom history during one-year follow-up and measured by number of patients in each group.
- ii. Presence of other cerebro-cardiovascular morbidity or mortality assessed by aggravation of patient status (mRS, modified Rankin Scale) at out-patient clinic during one-year follow-up and measured by the number of patients.

2) Secondary outcome:

- i. Changes in volumetric blood flow (ml/Sec) in quantitative MRA measured

by percentage change from the baseline study.

- ii. Changes in velocity (cm/Sec) in quantitative MRA measured by percentage change from the baseline study.
- iii. New FLAIR MR lesions assessed on one-year follow-up MRI and measured by the number of patients.

C. Sample size calculation

Assuming the proportion of 0.1 in the ginseng group and the proportion of 0.4 in placebo group in the analyses of primary and secondary outcomes, calculated sample size would be 29 patients each group for determining difference between two groups in the level of alpha of 0.05, power of 0.8 and 1:1 sampling ratio (equality test).

D. Randomization and follow-up of outcomes

There are two study groups as follows: a ginseng group as an intervention group, a promising placebo group as a control group. The participants will be randomly allocated to either the ginseng group or the placebo group by 1:1 ratio according to random permuted block with a block size of 20. Both groups will be followed up at 1, 3, 6 and 12 months after randomization. At each follow-up, history of the primary outcome, any adverse effects, any co-administration drugs, and study drug compliance will be evaluated. The secondary outcomes will be evaluated by comparison of the results of quantitative MR angiography studies performed at baseline and 12 months after randomization.

E. Study drugs and administration

Two study drugs are identical in appearance. In the intervention group, 2-gram ginseng per day (0.5 grams/capsule, 2 capsules twice a day) will be administrated for

12 months. In the control group, 2-gram placebo per day (0.5 grams/capsule, 2 capsules twice a day) will be administrated for 12 months.

F. Safety evaluation and reporting

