The follow-ups can be conducted in outpatient clinics or by telephone interview performed by experienced nurses since the presence of ischemic stroke or TIA history is asked, and mRS is evaluated in the interview. The investigators can do neurologic evaluations if needed.

9. Blood laboratory test and imaging test

A. Blood laboratory test

none

B. Imaging test

- 1) A quantitative MR angiography (QMRA) with noninvasive optimal vessel analysis (NOVA) for the changes of cerebral blood flow.
- 2) A brain MRI including FLAIR for the presence of new cerebral ischemic lesions.

10. Subject discontinuation (Drop-out)

- 1) Difficulty in administration of study drugs.
- 2) Impossible to follow up.

11. Patient data safety

Any identifiable human material and data will be excluded in the research. And a subject will be given a subject number. Collected data will be managed with a password by only the principle investigator and investigators. The data will be discarded after 3-year mandatory storage period.

12. Audit

The principle investigator will carry out inspections at finishing data collection and at

finishing data analysis.

13. Statistical analysis

The results will be analyzed in intention-to-treat method. For analysis of primary outcome, Fisher's exact test will be used for a dichotomized variable.

14. Detailed study schedule

Visits	Screening baseline	1 st F/U (Telephone/ OPD visit)	2 nd F/U (Telephone/ OPD visit)	3 rd F/U (Telephone/ OPD visit)	4 th F/U (Telephone/ OPD visit)
Date	0 day	1 month (± 2 weeks)	3 months (± 2 weeks)	6 months (± 2 weeks)	12 months (± 2 weeks)
Obtaining consent	●				
MR	●				●
Drug compliance		●	●	●	●

15. References

4) Lee CH, Kim J-H. A review on the medicinal potentials of ginseng and ginsenosides on cardiovascular diseases. *J Ginseng Res.* 2014;38:161-166

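### The 80% power in Section 7.C is claimed for the secondary outcomes too, but it was worked out for proportions and does not apply to percentage change in flow or velocity

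*Combined protocol and SAP*

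**What the plan says.** Section 7.C makes one calculation for the whole trial. Its inputs are "Assuming the proportion of 0.1 in the ginseng group" and "the proportion of 0.4 in placebo group in the analyses of primary and secondary outcomes", and the result is given "in the level of alpha of 0.05, power of 0.8 and 1:1 sampling ratio (equality test"). The conclusion covers both tiers of outcome: "in the analyses of primary and secondary outcomes, calculated sample size would be 29 patients each group".

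Section 7.B lists three secondary outcomes. The first is "Changes in volumetric blood flow (ml/Sec) in quantitative MRA measured" as percentage change from baseline. The second is "Changes in velocity (cm/Sec) in quantitative MRA measured by percentage change from the baseline study". The third, new FLAIR lesions at one year, is a number of patients. Section 7.H adds that flow is measured at several predetermined sites; it gives no rule for reducing these to one value per patient.

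Section 13 specifies intention-to-treat analysis and names one test. The sentence opens "For analysis of primary outcome" and prescribes Fisher's exact test. No test is named for any secondary outcome.

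**The concern.** A pair of proportions can describe an outcome that each patient either has or does not have. It cannot describe a mean percentage change in ml/sec or cm/sec unless a cut-off turns that change into responder or non-responder, and the plan has no such cut-off. Power for a continuous outcome needs a target difference and an SD (or their ratio), and neither is given. So for flow and velocity Section 7.C states a power for which the plan contains no calculation.

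This affects how the results are read. Section 2 presents collateral perfusion on quantitative MRA as the surrogate marker for the hypothesised effect, so readers will look closely at flow and velocity. A null result on either could be taken as the outcome of a comparison with 80% power, when the trial may have had a poor chance of detecting a moderate effect.

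**Working it through.** **Inputs from the plan (Section 7.C).** p1 = 0.1, p2 = 0.4, alpha 0.05, power 0.80, ratio 1:1, n = 29 per group. Sidedness is not stated; "equality test" is read as two-sided.

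**Step 1: reproduce the 29.** For two proportions with unpooled variance:

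n = (z0.975 + z0.80)² × [p1(1 − p1) + p2(1 − p2)] / (p1 − p2)²

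= (1.960 + 0.842)² × (0.09 + 0.24) / 0.09 = 7.849 × 0.33 / 0.09 = 28.78, rounded up to 29.

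The match is exact. Other common versions do not give 29: pooled variance 32, pooled with continuity correction 38, one-sided pooled 25, arcsine 29.8 (rounded up to 30). The arithmetic in Section 7.C is sound, and it is the arithmetic of one binary comparison.

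**Step 2: match it to the outcomes.**

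| Secondary outcome (7.B) | Scale | Can 0.1 vs 0.4 apply? |
|---|---|---|
| Flow, % change | continuous | No: no cut-off, SD or difference given |
| Velocity, % change | continuous | No: no cut-off, SD or difference given |
| New FLAIR lesions | number of patients | Yes in form, though no basis for the rates is given |

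**Step 3: what 29 per arm would give for flow and velocity.** The plan supplies no SD, so the difference has to be expressed in SD units. Assumptions: two-sided t-test at 0.05, one value per patient, all 29 per arm evaluable. Power comes from the noncentral t distribution with 2 × 29 − 2 = 56 degrees of freedom and noncentrality d × √(29/2).

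| True difference, d | Power |
|---|---|
| 0.3 SD | 20% |
| 0.5 SD | 46% |
| 0.749 SD | 80% |

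A normal approximation agrees closely: 2.802 × √(2/29) = 0.736 SD for 80% power.

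The plan gives no dropout rate. If 25 per arm had evaluable paired scans (an assumed figure), the same t-test would need about 0.81 SD for 80% power.

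**Step 4: is the 0.8 secure for the binary outcome?** The 28.78 rests on a normal approximation, whereas Section 13 plans Fisher's exact test. Summing the binomial probabilities of every 29-by-29 result with Fisher p ≤ 0.05, at 0.1 vs 0.4, gives exact power 0.68. A corrected Section 7.C should therefore not simply carry 0.8 forward for the primary outcome.

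**The case against.** The strongest reply is that little depends on this. The mismatch changes neither the sample size nor the primary analysis, and the plan already treats the flow measures as a surrogate and as an indirect measurement, which suits supportive use. That is fair, and it limits the point to a correction of what is claimed. It does not make the power statement true for flow and velocity.

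A second reply is that the 0.75 SD also rests on things the plan does not state: the test, roughly normal percentage changes, one value per patient, and complete follow-up. This stands. The figure has to be given with those conditions attached.

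A reader might also infer something stronger: that Section 7.C gives each secondary outcome its own test at 0.05, so that three uncontrolled tests carry a familywise error of 1 − 0.95³ = 14%. The documents do not support this. The 0.05 in Section 7.C is an input to a sample-size formula. Section 13 names no secondary test, and no success claim is tied to a secondary outcome. The count of three tests is inferred from the count of outcomes. The 14% also requires independence, although flow and velocity are probably correlated, and a true size of 0.05 for each test. Fisher's test, if it were used for FLAIR lesions, has exact size of only about 0.01 to 0.02 at 29 per arm for common event rates of 0.1 to 0.4. Requiring a formal multiplicity procedure here would be a preference, not the correction of an error.

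**Conclusion.** The point holds for the power statement. Section 7.C claims 80% power at 29 per group for outcomes that include two continuous measures, and the calculation behind it cannot apply to them as defined. That conclusion needs only Sections 7.B and 7.C. Its size is conditional: under the t-test assumptions in the working, 80% power is reached only at about 0.75 SD, and a half-SD effect would be missed more often than found (46% power).

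The 29 itself is not an arithmetical error, and new FLAIR lesions can be expressed as proportions. It should not be inferred that only the primary outcome was in view when the 29 was calculated, since the text says otherwise, nor that 80% is secure for the primary outcome under the planned test. The correction should be made, but it leaves the trial's design and its primary analysis as they are.

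**What to change.** In Section 7.C, remove the secondary outcomes from the power statement, or limit it to outcomes counted as numbers of patients. Add that the 29 rests on a normal approximation and that Fisher's exact test, as planned in Section 13, has about 68% exact power at 29 per group for 0.1 vs 0.4.

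For flow and velocity, state the detectable difference instead: about 0.75 SD at 80% power, with 46% power at 0.5 SD and 20% at 0.3 SD, assuming a two-sided 0.05 t-test, one value per patient and no dropout (about 0.81 SD if an assumed 25 per arm are evaluable).

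In Section 13, say that flow and velocity are supportive and will be reported as estimated between-group differences with 95% CIs, since Section 7.C will then claim no power for them.

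The cost is wording only, with no added patients, visits or scans. The downside is that the stated power becomes less favourable.

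### With 29 per group, the planned Fisher's exact test has about 68% power for 0.1 versus 0.4, not the stated 80%, before any drop-out

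*Combined protocol and SAP*

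**What the plan says.** Section 7.C gives the planning rates: "Assuming the proportion of 0.1 in the ginseng group and the proportion of 0.4 in placebo group". It applies them "in the analyses of primary and secondary outcomes" and arrives at "29 patients each group for determining difference between two groups in the level of alpha of 0.05, power of 0.8", with 1:1 allocation and the label of an equality test. It names neither the formula nor the test behind the 29, and it does not say in words whether alpha is one- or two-sided.

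Section 13 specifies intention-to-treat analysis and, for the primary outcome, says "Fisher's exact test will be used for a dichotomized variable". It names no other test.

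Section 10 lists two reasons for drop-out, one of which is "Impossible to follow up". No section gives an expected drop-out rate or an allowance for it in the sample size.

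Section 7.B lists three secondary outcomes. Two are percentage changes from baseline in quantitative MRA (volumetric flow and velocity). The third is the number of patients with new FLAIR lesions.

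**The concern.** A power statement holds only for the test that will be used. Fisher's exact test conditions on the total number of events and is markedly conservative with groups of about 30. A sample size taken from a normal-approximation formula can therefore fall well short of its nominal power.

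If so, a real 30-point difference would be missed more often than the protocol says, and a non-significant result would be reported as coming from an 80%-powered trial when it did not. Patients lost to follow-up would widen the gap. For the two quantitative MRA outcomes the question is whether Section 7.C provides any power basis at all.

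**Working it through.** **Inputs.** From Section 7.C: p1 = 0.10, p2 = 0.40, n = 29 per group, alpha = 0.05, power = 0.80, 1:1 allocation. From Section 13: Fisher's exact test. Two-sided testing is inferred (step 2).

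**Step 1. Reproduce the 29.** Unpooled normal approximation, two-sided:

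n = (z0.975 + z0.80)² × [p1(1−p1) + p2(1−p2)] / (p1−p2)²
= (1.960 + 0.842)² × (0.09 + 0.24) / 0.09
= 28.78, rounded up to **29**.

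The approximate power at 29 by this formula is 0.803, so the plan's figure is correct for this formula.

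**Step 2. Other formulas tried.**

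| Formula | n per group |
|---|---|
| Unpooled, two-sided | 29 |
| Arcsine, two-sided | 30 |
| Pooled, two-sided | 32 |
| Pooled with continuity correction, two-sided | 38 |
| Unpooled, one-sided | 23 |
| Pooled, one-sided | 25 |
| Pooled with continuity correction, one-sided | 32 |

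Only the unpooled two-sided formula returns 29. That supports reading alpha as two-sided, as does the label of an equality test.

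**Step 3. Exact power at 29 per group.** Sum the probabilities Binomial(29, 0.1) × Binomial(29, 0.4) over all tables that the test rejects at 0.05:

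| Test | Power | Maximum type I error |
|---|---|---|
| Fisher, two-sided (planned) | **0.681** | 0.025 |
| Uncorrected chi-square | 0.778 | not computed |
| Boschloo's unconditional exact test | 0.776 | 0.048 |

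The type II error with Fisher's test is 1 − 0.681 = 0.319. Its maximum size of 0.025 means that about half of the nominal 0.05 is unused.

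**Step 4. Fisher power at other group sizes, same rates.**

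| n per group | Fisher power |
|---|---|
| 23 (29 × 0.8 = 23.2; assumed 20% loss) | 0.575 |
| 26 (29 × 0.9 = 26.1; assumed 10% loss) | 0.616 |
| 29 | 0.681 |
| 32 | 0.748 |
| 35 | 0.785 |
| 36 | 0.800 |

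Reaching 80% takes 36 per group, or 72 in total against the planned 58, before any allowance for losses.

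**Step 5. Effect needed at 29 per group.** Fisher's test reaches about 80% only if the rates are 0.071 versus 0.40 (0.802) or 0.10 versus 0.445 (0.799).

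**Step 6. Secondary outcomes.** Power for a mean percentage change needs an expected difference and a standard deviation. The protocol gives neither for flow or velocity, and it defines no dichotomy of them to which 0.1 and 0.4 could refer. The FLAIR outcome is binary, so proportions can apply to it, although Section 13 names no test for it.

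**The case against.** - **The 29 is not a miscalculation.** This is right. It is the correct answer from a standard formula, and Section 7.C does not claim it was derived for Fisher's test. The fault is the mismatch with Section 13, and rounding or choice of approximation does not explain a gap of about 12 points.
- **Fisher's test protects the type I error.** Also right: no positive result is undermined. Only the stated power is wrong.
- **Sidedness is not stated.** One-sided Fisher at 0.05 would give 0.781, close to the claim. But the one-sided formulas give 23, 25 or 32, not 29, so this reading does not fit the plan's own number.
- **Intention-to-treat and telephone follow-up limit the loss.** Partly right. A patient who stops the capsules can still supply an outcome. A patient who cannot be followed up does not, and Section 13 has no rule for missing outcomes. The 10% and 20% losses are assumptions; the 0.681 assumes no loss.
- **It is late.** The protocol is a final version dated March 02, 2018, and the study is expected to end on July 31, 2018. If that date includes the 12-month visit (± 2 weeks), randomization would have closed by about mid-August 2017. This argues against asking for more patients and calls for care in changing the primary test. It does not make the stated power correct.

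**Conclusion.** The concern holds. At the plan's own rates and group size, the planned test has power 0.681, about 12 points below the stated 0.80. A true difference of 0.1 versus 0.4 would be missed about one time in three. This rests on two-sided testing at 0.05, complete outcome data and the rates in Section 7.C; any loss of outcomes spread over both groups lowers the figure further. The power claim for the two quantitative MRA percentage-change outcomes has no basis in the document. What is wrong is the power statement, not the arithmetic behind 29 and not the validity of Fisher's test.

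**What to change.** **Required.** Restate Section 7.C: with 29 per group and a two-sided Fisher's exact test at 0.05, power is about 68% for 0.1 versus 0.4, and about 62% if 10% of outcomes are missing (marked as an assumed rate). Say that the test is two-sided and which primary outcome the figure describes, since Section 7.B lists two and Section 7.G names only ischemic symptoms. Delete the claim that the calculation covers the quantitative MRA outcomes.

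**Optional.** Replace Fisher's test in Section 13 with Boschloo's unconditional exact test. At 29 per group this keeps exact type I error control (maximum size 0.048) and gives power 0.776, which Section 7.C would state as about 78% with no losses. With the same assumed losses it is about 0.715 at 26 per group and 0.636 at 23, so these should be given too. Because this changes the primary test, it must be documented and fixed before unblinding. If that is no longer possible, keep Fisher's test with the corrected power.

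**Cost.** Wording in Section 7.C, and in Section 13 if the test changes. No extra patients. The stated power becomes less favourable.

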CLINICAL STUDY PROTOCOL

Title: Preventive Effects of Ginseng against Atherosclerosis and Subsequent ischemic Stroke:

A randomized controlled trial

(PEGASUS)

Study Type: Single-center, Randomized, Double-blind, Placebo-controlled trial; Investigator-initiated trial

Protocol Number: KGC2026-26

NCT Number: NCT02796664

Version of the document: 6.3, Final version

Date of the document: March 02, 2018

1. Ethical considerations

This trial will be conducted in compliance with Good Clinical Practice (GCP) and Declaration of Helsinki. This trial will start after the written approval of the institutional review board (IRB) of our institution is obtained.

2. Introduction or background information

Atherosclerotic stenosis in a cerebral artery progressing more than 70% caused cerebral ischemia, leading to developing collateral circulation. Ischemic symptoms of a patient are varying by the development of collateral circulation, which is caused by not only anatomical differences but also angiogenesis factors. Recent study reported that Korean red ginseng (KRG) had a good effect on cardiovascular system by affecting nitric oxide (NO). Endothelial nitric oxide synthase (eNOS) was studied a lot because that NO produced by eNOS was associated with anti-inflammation and anti-atherosclerosis. Moreover, KRG was reported that it had a vasodilation effect, a blood pressure stabilizing effect and an anti-platelet effect such as reducing platelet aggregation. Several effects mentioned above suggests that KRG had the preventive effect in cardiovascular system and ischemic cerebral stroke.

Therefore, we hypothesize that ginseng has prevention effects against atherosclerosis and subsequent ischemic stroke. The preventive effects of ginseng on cerebral ischemic stroke will be evaluated in the group of the patients with advanced atherosclerosis such as severe stenosis or occlusion in the intracranial arteries. In addition, the changes of collateral perfusion state on an ischemic territory caused by atherosclerosis will be evaluated using

quantitative magnetic resonance angiography as a surrogate marker.

3. Literature review

- A. Some reports showed that ginseng had a good effect on cardiovascular system through affecting NO.
- B. It was reported that NO produced by endothelial nitric oxide synthase (eNOS) was related to anti-inflammation and anti-atherosclerosis.

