- C. Ginseng had effects of reducing platelet aggregation, lowering mean systolic pressure, and vasodilatation.

4. Study objectives and purpose

The aim of this trial is to study prevention effects of ginseng against atherosclerosis and subsequent cerebral ischemic stroke in high-risk patients with severe steno-occlusive lesions in internal carotid artery, middle cerebral artery, and posterior circulation.

5. Expected study duration

From the date of institutional review board (IRB) approval to July 31, 2018.

6. Study subjects

A. Selection criteria

1) Inclusion criteria

- i. Aged between 20 and 80.
- ii. Severe stenosis or occlusion at an internal carotid artery, middle cerebral artery and vertebrobasilar system in cerebral angiography.
- iii. Any stroke risk factors such as hypertension, diabetes, hyperlipidemia, smoking and alcohol drinking.
- iv. No adverse effect history of ginseng administration.

2) Exclusion criteria

- i. Genetic cerebrovascular diseases.
- ii. Adverse reaction to contrast medium.
- iii. Pregnant women.
- iv. History of previous intra-arterial thrombolysis, cerebral angioplasty and/or stenting, carotid endarterectomy, and bypass surgery.
- v. History of cardioembolic stroke or possibility of cardioembolic stroke.
- vi. Possibility of cancer stroke.
- vii. Renal failure (GFR < 30 ml/min) or liver disease.

B. Risk and benefit evaluation

- 1) Potential risk of this study: Although additional risks are considered as minimal, potential risks participating in this trial are showed as follows: any adverse effects related to ginseng; pain, bruise or hematoma at puncture site, dizziness, syncope, or infection related to cerebral catheter angiography.
- 2) Potential benefit of this study: Although there would be no potential benefit for

participants, their participations in this trial would help medical advancements.

- 3) Conclusion of risk and benefit analysis: It is considered that a potential benefit would be bigger than a potential risk because of less adverse effect of ginseng on subjects, and an important suggestion to future treatment.

C. Eligible patients

Any inpatients or outpatients who are referred to the department of radiology for transfemoral cerebral angiography will become eligible patients. Among them fulfilled selection criteria, investigators will obtain written informed consent individually.

7. Study design

A. Type of a trial design

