If any adverse effects are occurred, the participants will report the problem to an investigator. The investigator will appoint outpatient clinic. When the subject visits the outpatient clinic, the investigator will evaluate allergic symptoms such as redness, swelling, respiratory difficulty and grade the symptom severity. The investigator will gather other subject symptoms as patient says.

G. Primary outcome evaluation

The presence of any cerebral ischemic symptoms is the primary outcome. The history of cerebral ischemic symptoms includes transient ischemic attack (TIA) and cerebral ischemic infarction. If the related history is reported, a diffusion-weight MRI will be performed. It will be evaluated whether new ischemic lesion is related to the steno-occlusive lesion confirmed by cerebral angiography at baseline.

H. Secondary outcome evaluation

A quantitative MR angiography (QMRA) with noninvasive optimal vessel analysis (NOVA) will be performed for evaluating secondary outcomes at baseline and 12 months after randomization. QMRA with NOVA will measure blood flow at the predetermined sites. The results would become an indirect measurement of collateral flow state of a steno-occlusive vascular lesion.

8. Data collection forms and items

Subject No.	Sex	Age	Results of cerebral catheter angiography			The presence of acute ischemic lesions
			The presence of a steno-occlusive lesion at internal carotid artery, middle cerebral artery, and vertebrobasilar system	Stenosis severity (Severe/moderate/mild)	Complete total occlusion	

Medication Information				
Duration (mo)	Dose	Date Start	Date End	Compliance

※ Compliance

Drug name	Expected administration days	Actual administration days	Compliance (%)
Ginseng			
Placebo			

Non-invasive Optimal Vessel Analysis (NOVA) (at baseline)	Non-invasive Optimal Vessel Analysis (NOVA) (at 12 months after randomization)

Brain-MRI (New lesions on FLAIR) (at baseline)	Brain-MRI (New lesions on FLAIR) (at 12 months after randomization)

The presence of any ischemic stroke history at 3 months follow-up	The presence of any ischemic stroke history at 6 months follow-up	The presence of any ischemic stroke history at 9 months follow-up	The presence of any ischemic stroke history at 12 months follow-up

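### Section 7.D promises a review of adverse effects and co-medication at every contact, but 7.F grades only allergic symptoms and Sections 8, 13 and 14 give no clear place to record, schedule or compare the rest

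*Combined protocol and SAP*

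**What the plan says.** Section 7.D sets follow-up at 1, 3, 6 and 12 months and states: "At each follow-up, history of the primary outcome, any adverse effects, any co-administration drugs, and study drug compliance will be evaluated".

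Section 7.F describes how safety is evaluated. It begins with the participant: "If any adverse effects are occurred, the participants will report the problem to an investigator". At the clinic visit that follows, "the investigator will evaluate allergic symptoms such as redness, swelling, respiratory difficulty and grade the symptom severity". On everything else it says: "The investigator will gather other subject symptoms as patient says".

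On pharmacology, Section 2 says of Korean red ginseng that "it had a vasodilation effect, a blood pressure stabilizing effect and an anti-platelet effect such as reducing platelet aggregation", and Section 3.C says: "Ginseng had effects of reducing platelet aggregation, lowering mean systolic pressure, and vasodilatation". Capsules are taken for 12 months by patients with severe stenosis or occlusion (Sections 6.A and 7.E). The favourable risk-benefit conclusion in Section 6.B leans on ginseng having few adverse effects.

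Section 8, "Data collection forms and items", has blocks for angiography, medication and compliance, NOVA, FLAIR lesions and stroke history. The text after the tables describes the clinic or telephone interview as covering stroke or TIA history and mRS. Section 9.A plans no blood tests. Section 14 has three rows: consent, MR and drug compliance. Section 13 names intention-to-treat analysis and Fisher's exact test for the primary outcome, and says nothing on safety.

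**The concern.** The plan makes a general promise in one section and describes a narrower procedure in another. Staff who work from 7.F, the form and the schedule would ask about stroke, TIA, mRS and compliance, and would grade allergic symptoms if a participant reported a problem. They would have no prompt for the kinds of harm that the protocol's own account of ginseng makes foreseeable, and no marked place to write one down.

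Two things are at stake. First, a report of no safety signal would be hard to interpret, because a reader could not tell absence of events from absence of systematic enquiry. Section 6.B rests on a premise about adverse effects that a randomised, placebo-controlled comparison is well placed to examine. Second, a bleeding event cannot be interpreted without knowing what else the patient was taking. The documents neither describe nor exclude background antithrombotic treatment, so its use is an assumption here. That uncertainty is itself a reason to record it.

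**Working it through.** **Step 1. Trace the 7.D promise through the other sections.**

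| Place | Adverse effects | Co-administered drugs |
|---|---|---|
| 7.D, follow-up | Any, at 1, 3, 6 and 12 months | Any, at the same contacts |
| 7.F, safety | On participant report; allergic symptoms named and graded; others as volunteered, no grade stated | Not mentioned |
| 8, form | No field | No clear field |
| 8, interview description | Not mentioned | Not mentioned |
| 14, schedule | No row | No row |
| 13, analysis | None | None |

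The promise appears once. The form, the interview description, the schedule and the analysis section do not carry it forward.

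**Step 2. Check the medication block.** The Medication Information block in Section 8 asks for duration, dose, start, end and compliance. It has no drug-name column, and the compliance table after it lists only ginseng and placebo. It most likely means study drug. That is a reading, not a certainty.

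**Step 3. Ask where a non-allergic harm would end up.**
- If it is cerebro-cardiovascular morbidity or death and worsens mRS, it counts under primary outcome ii (Section 7.B) and is compared by arm.
- If it is symptomatic but leaves mRS unchanged, it may surface under 7.D or be volunteered under 7.F. No grade, field or table is specified for it.
- If it is an asymptomatic change in blood pressure, nothing described would detect it.

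**Step 4. Scale.** The planned size reproduces. With proportions 0.1 and 0.4, unpooled variance, two-sided alpha 0.05 and power 0.8:

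n = (0.1 × 0.9 + 0.4 × 0.6) × (1.960 + 0.842)² / 0.3² = 28.78 (unrounded normal quantiles), rounded up to 29 per group.

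With zero events recorded among 29 ginseng patients, the one-sided exact 95% upper limit is 1 − 0.05^(1/29) = 0.098, or 9.8%. This holds even with perfect recording, so it reflects the sample size and not the gap in Step 1.

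The documents give no adverse-event rates. For assumed true rates p, the chance of at least one event in the arm is 1 − (1 − p)^29 and the expected count is 29p:

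| Assumed p | At least one event | Expected count |
|---|---|---|
| 1% | 25% | 0.29 |
| 2% | 44% | 0.58 |
| 5% | 77% | 1.45 |
| 10% | 95% | 2.90 |

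Over this range fewer than three events are expected in the ginseng arm, so each one missed or left ungraded matters.

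**The case against.** A reader might infer from 7.F that allergic symptoms are the only ones actively evaluated and that other harms would not be counted at all. The documents do not support that. Section 7.D requires a scheduled, unrestricted review at four contacts, and 7.F itself gathers other symptoms. Serious cerebro-cardiovascular events that worsen mRS, and deaths, fall under primary outcome ii. This objection stands, and it limits the point to how harms are elicited, graded, recorded and compared.

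A reader might also take bleeding to be an effect that the protocol attributes to ginseng. It is not. Haematoma, dizziness and syncope appear only as risks of catheter angiography in Section 6.B. The step from reduced platelet aggregation to bleeding is a reasonable inference, but it belongs to this review.

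The form may not be the complete case report form. It has no mRS field, although mRS defines part of the primary outcome, so a missing field does not prove that the data go unrecorded. This also stands. It does not rescue 7.F, which states a grading method for allergic symptoms only, or Section 13, which plans no comparison of harms. The form's stroke-history columns are at 3, 6, 9 and 12 months against contacts at 1, 3, 6 and 12, so it cannot be assumed to follow 7.D.

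Finally, one might divide the 9.8% limit by an assumed capture rate to size the loss. No document supports any such rate, and the calculation would presume spontaneous reporting alone, which 7.D contradicts.

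**Conclusion.** The concern holds as an inconsistency between 7.D and Sections 7.F, 8, 13 and 14. As written, non-allergic harms plausibly linked to the anti-platelet, blood-pressure and vasodilatory effects cited would be elicited unsystematically and left ungraded. They would not be compared by arm unless they entered primary outcome ii through a worsened mRS or death.

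The consequence is uncertain capture and reporting of harms, not their certain loss, and its size cannot be derived from the documents. The conclusion rests on three readings: that bleeding follows plausibly from the anti-platelet claim, that the Medication Information block means study drug, and that no fuller form exists outside the documents. If a fuller form does exist, the missing fields fall away, but the limited grading in 7.F and the absent analysis in Section 13 remain. The change is worth making because it is cheap and concerns patient safety; it does not affect the validity of the primary comparison.

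**What to change.** Reconcile 7.F, 8, 13 and 14 with 7.D:

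- **7.F:** keep the open enquiry about any adverse effect. Add a short set of solicited questions at the existing 1, 3, 6 and 12-month contacts, covering bleeding or bruising, dizziness or syncope, and allergic symptoms. Grade the severity of every adverse event.
- **Section 8:** add adverse-event fields (date, type, severity) and a co-medication field that names each drug and identifies any antithrombotic. Label the existing medication block as study drug if that is what it is. Add both items to the interview description.
- **Section 14:** add rows for adverse events and co-medication at each follow-up.
- **Section 13:** add a tabulation of adverse events by arm.

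This needs no new visits, tests or staff. Interviews become slightly longer, and more minor events will be recorded in both arms. Asymptomatic blood-pressure change would still not be captured, since no measurement is planned and contacts may be by telephone; the report should state that limit.
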